Thus, the advantages of nucleos(t)ide analogue therapy are the ease of administration, the lack of significant side effects and the consistent suppression of HBV DNA that can be achieved, particularly with the newer agents such as tenofovir DF and entecavir. While emergence of drug resistance can limit the efficacy of oral agents, a low rate of antiviral resistance (1% or less even with prolonged therapy for 4 to 5 years), is seen with entecavir and tenofovir DF, reflective of their greater potency and higher genetic barrier to resistance. As a consequence 80-90% of patients treated long-term with these agents achieve rates of marked suppression of HBV DNA levels and normal ALT levels. The advantage of peginterferon therapy is that it is administered for a limited period (6 to 12 months) and results in loss of HBsAg in a significant proportion of patients. Previous studies have shown that a one-year course of combination therapy of peginterferon and nucleos(t)ide analogue does not yield a higher response rate than a one-year course of either agent alone (21). However, these studies have been limited by the use of a nucleos(t)ide analogue with high risk of resistance (e.g. lamivudine) and a relatively short course of treatment. Thus, an obvious question is whether the combination of a limited course of peginterferon (6 or 12 months) with long-term therapy with a potent nucleos(t)ide analogue (tenofovir DF or entecavir for at least 4 years) will provide a higher rate of loss of HBsAg and ability to stop therapy without relapse. This clinical trial compares the efficacy of peginterferon plus a potent nucleotide analogue, tenofovir DF, for 24 weeks followed by monotherapy with tenofovir DF for a further 3.5 years to the efficacy of that same potent nucleotide analogue, tenofovir DF, given for a full 4 years. The primary measure of outcome will be HBsAg loss in serum 240 weeks after starting antiviral therapy.

2. Study objectives

To define the role of limited duration peginterferon alfa-2a in the presence of tenofovir for treating people with chronic hepatitis B by:

- Evaluating “off treatment” sustained responses following combination therapy consisting of peginterferon alfa-2a plus tenofovir DF versus tenofovir DF monotherapy.
- Comparing the on-treatment efficacy of initial treatment with combination therapy consisting of peginterferon alfa-2a plus tenofovir DF versus tenofovir DF monotherapy.

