2.1. Primary Endpoint

HBsAg loss at week 240.

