8.1. Statistical analysis

Summary statistics will be generated to describe the study sample at baseline. Descriptive statistics, including measures of central tendency (e.g. means, medians) and estimates of spread (e.g., standard deviations, quartiles) will be used for continuous variables such as age and baseline HBV DNA and HBsAg levels. Frequency distributions will be used for categorical variables such as HBV genotype and HBeAg status. Ninety-five percent confidence intervals will be calculated for all point estimates of continuous data. Graphical displays (e.g. histograms, box plots) will also be used to describe the data. The baseline demographic information and viral characteristics will be compared between the two treatment arms using the chi-square test for association or exact tests for differences in proportions for categorical variables or using a test of trend

in ordinal data. Continuous variables may be transformed, where appropriate, to meet the assumptions of parametric tests. The Student's t-test or a non-parametric alternative, the Wilcoxon rank-sum test, will be used to determine differences in the distribution of continuous data between the two treatment arms.

Primary analyses will be performed using all enrolled participants (intention-to-treat analysis). Participants will be considered enrolled in the study upon being randomized to one of the two treatment arms.

For all analyses, a p-value of less than 0.05 will be used to indicate statistical significance.

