8.1.1. Analysis of primary endpoint

The primary endpoint is loss of HBsAg at week 240. The cumulative proportion of HBsAg loss at the designated time-point will be estimated using the product-limit (Kaplan-Meier) estimate. HBsAg loss between two treatment groups will be compared using a Wald-type two-sided two-sample proportion test (chi-square test).

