8.1.2.1. Analyses of other secondary endpoints

Secondary endpoints for this clinical trial are listed in sections 2.2.1 – 2.2.9. These endpoints could be grouped into several different classes. The first group of endpoints we will deal with are binary endpoints characterized by the occurrence of some event by a fixed time point. These events include HBeAg loss, HBeAg seroconversion, HBsAg seroconversion, normalization of ALT, ALT \leq 1.25 X ULN, HBV DNA $<$ 1000 IU/mL, HBV DNA $<$ 20 IU/mL, absence of detectable antiviral drug-resistance HBV mutations, treatment discontinuation, and treatment failure. Analysis will be conducted separately for these events at the designated time points listed in sections 2.2.1-2.2.9

Proportion of such an event (e.g. proportion of HBeAg loss) between two treatment groups will be summarized using 95% confidence intervals and will be presented graphically by using bar charts. The rate of occurrence of an event between two treatment groups will be compared using a two-sided two-sample proportion test (chi-square test or Fisher's exact test as appropriate). We will also describe the treatment effects using relative risk of the event and corresponding 95% confidence interval. In order to take into account the stratification at randomization, we will use Mantel-Haenszel chi-square test. Comparison of rates of an event across two treatment groups adjusting for other baseline demographic, virological and clinical characteristics such as

age, race, genotype, HBeAg status, initial HBV DNA level, and baseline histology will be performed using multivariable log-linear (Poisson) regression, with HBsAg loss (Yes/No) as the outcome. The results will be presented as relative risks of the event and their 95% confidence intervals.

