The third group of variables consists of variables that are measured over time (longitudinal data) such as quantitative HBV DNA levels. For graphical representation over time, we will use spaghetti plots of original data (e.g. HBV DNA levels) and summarize the pattern of data across subgroups (e.g. genotype, treatment groups) over time by using means (for continuous outcome) or proportions (for binary outcomes). To determine the significance of change in continuous outcome over time across treatment group adjusting for other baseline and longitudinal participant characteristics, we will use mixed models if the data are normally distributed or generalized estimating equations (GEE) if deviation from normality is evidenced. These approaches simultaneously model the regression of the response variable on the independent variables and account for the correlated nature of the responses. Analyses using conventional regression methods could provide erroneous variance estimates and loss of statistical efficiency because of the conventional assumption that each response is statistically independent. As a result, invalid inferences could be made if the conventional approach were applied to these longitudinal data. A similar approach of analysis will be adopted (generalized linear mixed model or GEE) for longitudinal binary or count outcomes over time.

The results will be summarized using rate of change/odds ratio/relative risk over time and the corresponding confidence intervals. Interaction between treatment and participant characteristics will be investigated to assess the differential effect of treatments across subgroups of participants (e.g. genotypes).

Secondary endpoints that are defined within a specific subgroup will be analyzed only for participants in that subgroup. For example, sustained off treatment (36 and 48 weeks after end of treatment) responses will be assessed only among those whose treatment was discontinued at week 192.

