8.3. Sample size and power

The sample size for this study was determined based on the primary endpoint of HBsAg-loss at 48 weeks after treatment has been stopped. There are no data available on HBsAg loss for long-term treatment with tenofovir DF or tenofovir DF and peginterferon combination therapy. We anticipate that after 192 weeks of treatment and 48 weeks of follow-up post-treatment 5% of the participants in the tenofovir DF alone group will achieve HBsAg loss compared to 15% participants in the tenofovir DF and peginterferon combination therapy group. The clinical trial would require 141 participants per arm (282 participants in total) to detect this expected difference with 80% power at 5% level of significance using a two-sided test of equality between two proportions (chi-square test). However, for this long-term treatment trial, it is expected that approximately 25% of the participants will be lost to follow-up and hence the study will recruit a total of 376 participants (randomized 1:1 to two treatment arms, 188 per arm) to account for the missing participants.

9. Data and safety monitoring board

Data and safety will be monitored by the NIDDK in conjunction with an NIDDK-appointed Data and Safety Monitoring Board (DSMB). This board serves in a consultative capacity to inform the NIDDK decisions regarding conduct of the study. The description of DSMB activities is included in the DSMB Charter.

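### Section 8.1 lets p<0.05 declare significance for every analysis, including 22 between-arm efficacy secondary endpoints and an open set of interactions, with no testing order or exploratory label

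*Combined protocol and SAP*

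**What the plan says.** Section 2.1 names one primary endpoint, "HBsAg loss at week 240". Section 8.1.1 tests it two-sided, and the sample size section builds the trial on that test at the 5% level. Section 9.1 plans no interim look at efficacy.

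For everything else, section 8.1 states: "For all analyses, a p-value of less than 0.05 will be used to indicate statistical significance". Section 8.1.2.1 then says of the binary secondary events: "Analysis will be conducted separately for these events at the designated time points listed in sections 2.2.1-2.2.9", and compares their rates between the two treatment groups. Section 8.1.2 compares cumulative HBsAg loss (2.2.1a) between arms by a stratified log-rank test. The longitudinal part of 8.1.2.1 adds: "Interaction between treatment and participant characteristics will be investigated to assess the differential effect of treatments across subgroups of participants", with genotype as the only example and no list of characteristics.

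The text available for review does not rank the secondary endpoints, split alpha among them, make them conditional on the primary result, or call them or the interactions exploratory.

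**The concern.** The wording in 8.1 is an affirmative rule, not a silence that convention can fill. Read literally, a secondary p-value of 0.04 has the same standing as a primary p-value of 0.04.

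This matters because a stated study objective depends largely on the secondary list. Section 2 includes "Comparing the on-treatment efficacy of initial treatment with combination therapy consisting of peginterferon alfa-2a plus tenofovir DF versus tenofovir DF monotherapy", and the on-treatment measures are mainly the ten week-192 endpoints in 2.2.1. The sample size section also says that no data exist on HBsAg loss with either long-term regimen, so a primary result that misses significance is a real possibility. If it does, a report that follows 8.1 could still describe a difference in HBeAg loss, ALT, HBV DNA or one genotype as statistically significant. A reader weighing such a result against the peginterferon side effects described in 5.3.3 would have nothing in the plan to separate a controlled finding from a chance one.

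**Working it through.** **1. The primary test and its alpha.** Inputs from the sample size section: "5% of the participants in the tenofovir DF alone group will achieve HBsAg loss" against 15% with combination therapy, two-sided 5% level, 80% power. With mean rate 0.10:

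n per arm = [1.960 × √(2 × 0.10 × 0.90) + 0.842 × √(0.05 × 0.95 + 0.15 × 0.85)]² / 0.10² = 140.1, rounded up to 141.

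Total 282, and 282 / (1 − 0.25) = 376. Both match the plan. The full 5% is spent on one endpoint with no interim efficacy look, so the primary error rate is 5% whatever happens below it.

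**2. Count of between-arm efficacy secondary endpoints.**

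| Section | Items |
|---|---|
| 2.2.1 (week 192), a to j | 10 |
| 2.2.2 (week 240), a to g | 7 |
| 2.2.3 (off treatment), a to d | 4 |
| 2.2.7 (treatment failure) | 1 |
| Total | 22 |

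Each 2.2.3 item is counted once, although it is read at both 36 and 48 weeks. Two groups are left out:
- The 21 items in 2.2.4 to 2.2.6 are worded as contrasts between end-of-treatment HBsAg or HBV DNA groups, so an inactive peginterferon would not make them null.
- The items in 2.2.8 and 2.2.9 are safety endpoints, which can differ between arms even if peginterferon adds no efficacy.

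**3. Error rate if peginterferon adds no efficacy.** Each of k tests is taken as a standard normal z-statistic with common pairwise correlation ρ (an assumption) and two-sided cut-off 1.96.

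- Independent tests: 1 − 0.95^22 = 0.68 for any significant result; 1 − 0.975^22 = 0.43 for one favouring peginterferon.
- Correlated tests: 1 − ∫ [Φ((1.96 − √ρ·w)/√(1−ρ)) − Φ((−1.96 − √ρ·w)/√(1−ρ))]^k φ(w) dw. For the benefit direction, the second Φ term is omitted.

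| ρ assumed | Any of 22, two-sided | False benefit among 22 | Any of the ten week-192 endpoints, two-sided |
|---|---|---|---|
| 0 | 68% | 43% | 40% |
| 0.3 | 57% | 30% | 35% |
| 0.5 | 44% | 22% | 29% |
| 0.7 | 30% | 15% | 21% |
| 0.9 | 16% | 8% | 13% |

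The nominal rates are 5% two-sided and 2.5% in the benefit direction. At ρ = 0.9 both are still about three times nominal (15.9/5 and 7.95/2.5, each 3.2). At ρ = 0.5 they are about nine times nominal (8.8). The expected number of false positives is 22 × 0.05 = 1.1 at any correlation.

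**4. Interactions.** They fall under the same 0.05 rule, but the plan does not list the characteristics or outcomes to be tested, so their contribution cannot be calculated.

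**The case against.** The strongest reply is that the plan already has the structure that matters: one primary endpoint, labels of primary and secondary, a sample size tied to the primary, no interim efficacy look, and a commitment in 8.1.2 and 8.1.2.1 to estimates with 95% confidence intervals. On that view, secondary already means supportive. The description of the structure is right, and it is why the primary conclusion is safe. The inference fails because the sentence in 8.1 expressly reaches every analysis.

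A second reply is that the endpoints overlap heavily. This stands. HBV DNA below 20 IU/mL is nested in below 1000, normal ALT in the 1.25 × ULN criterion, and seroconversion in antigen loss; 2.2.2a nearly repeats the primary. Rare outcomes tested by Fisher's exact test also have a true size below 5%. Both facts point to the lower part of the range.

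A reader might also infer more than the documents support:

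- **That all the items in 2.2 count as chances for a false peginterferon claim.** The exclusions above show otherwise. The between-group wording of 8.1.2.1 does leave some doubt about how 2.2.4 to 2.2.6 will be tested, but that is a separate matter of clarity.
- **That a false claim is likely.** At correlation 0.5 the figure for the 22 endpoints is below one half, and for a false benefit below one quarter.
- **That the number of interaction tests can be read from the covariates named in 8.1.2 and 8.1.2.1.** Those are adjustment variables; the interaction sentence does not refer to them.
- **That no test is designated for each endpoint.** Section 8.1.2 names the stratified log-rank test for 2.2.1a. Section 8.1.2.1 names chi-square or Fisher's exact test for binary endpoints, then adds stratified and adjusted analyses.
- **That the plan authorises an efficacy claim after a failed primary.** No sentence says so. The plan simply has nothing that prevents it.

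**Conclusion.** The point holds for secondary and subgroup claims and does not touch the primary conclusion. Under the plan as written, with no efficacy from peginterferon, the chance of at least one significant result among the 22 between-arm efficacy endpoints is about 44% (16% to 68%). The chance of a false benefit is about 22% (8% to 43%).

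These figures rest on an equal-correlation normal model, tests of exact 5% size, and an assumed correlation of 0.5 with a range from 0.9 to 0. The documents supply no correlation. The conclusion does not depend on the value chosen, because the rate is still about three times nominal at 0.9. Interactions add an amount that cannot be computed.

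Unadjusted secondary testing is acceptable when declared exploratory; the defect is that the plan declares the opposite. It should be corrected, but it does not threaten the trial's main answer.

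**What to change.** Replace the significance sentence in section 8.1 with wording such as:

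*Statistical significance at two-sided 0.05 is declared only for the primary comparison in 8.1.1. Secondary endpoints and all interaction or subgroup analyses are exploratory. They are reported as estimates with 95% confidence intervals; any p-values are nominal and not used to claim efficacy.*

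If the sponsor wants formal secondary claims, it may instead prespecify a short fixed sequence of endpoints of its own choosing, tested only after a significant primary result and stopped at the first non-significant one. That keeps the chance of any false formal claim at or below 5%. Which endpoints enter it, and whether to have one at all, is the sponsor's decision.

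The cost is one sentence of text. Sample size, visits, the primary test and its power are unchanged, and safety results are still reported in full. The real downside is that isolated secondary or subgroup results can no longer be called statistically significant.

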8.1.1. Analysis of primary endpoint

The primary endpoint is loss of HBsAg at week 240. The cumulative proportion of HBsAg loss at the designated time-point will be estimated using the product-limit (Kaplan-Meier) estimate. HBsAg loss between two treatment groups will be compared using a Wald-type two-sided two-sample proportion test (chi-square test).

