A feature of peginterferon treatment that is distinctly greater than with nucleos(t)ide analogue therapy is the loss of HBsAg. Thus, in studies of HBeAg-positive chronic hepatitis B with a one-year course of peginterferon, rates of loss of HBsAg have ranged from 3% to 7%, whereas loss of HBsAg with a 48 week course of nucleos(t)ide analogues is <1% to 3% (12-16). Furthermore, long-term follow up of patients who have become HBeAg-negative after interferon therapy has shown that the majority of these patients eventually become HBsAg negative as well (20). This gradual loss of HBsAg is greater than occurs spontaneously and appears to be a special characteristic of responses to peginterferon therapy. Emerging data suggests that ultimately prolonged suppression of viral replication with a nucleos(t)ide analogue leads to HBsAg loss. In one study loss of HBsAg after 1 year of tenofovir DF was observed in 3% of those treated for HBeAg-positive CHB and this figure increased to 6% after 2 years of therapy (only in genotypes A and D). In another study with adefovir for 4-5 years for HBeAg-negative CHB, HBsAg clearance occurred in a third of the patients followed for up to 5 years after stopping therapy. It is unknown whether even longer duration of therapy with nucleoside(t)ide analogues will result in ever increasing HBsAg loss or whether the rate of loss will level off.

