This is a randomized (1:1) parallel group design trial comparing outcomes of treatment with (i) monotherapy, i.e., tenofovir DF 300 mg daily for 192 weeks (4 years) and (ii) combination therapy, i.e., peginterferon alfa-2a 180 μ g weekly for 24 weeks plus tenofovir DF 300 mg daily for 192 weeks (4 years). Enrolled participants will be stratified by HBeAg status (positive/negative), known genotype (A vs. all others) and cirrhosis (present vs. absent). After 192 weeks of treatment, participants meeting criteria for treatment discontinuation will stop treatment and be followed for up to 48 weeks (total duration of treatment and follow up is up to 240 weeks). Emtricitabine/tenofovir coformulated as Truvada, approved for treating HIV but not for treating HBV infection, will be offered to participants with primary nonresponse, partial virological response or confirmed virologic breakthrough.

4. Study population

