8.1.2. Analysis of secondary endpoints

Analysis of secondary endpoint listed in 2.2.1a: *To compare the cumulative proportion HBsAg loss over time during and after treatment*

Cumulative proportion of HBsAg loss over time will be calculated using the product limit (Kaplan-Meier) method. HBsAg loss between two treatment groups will be compared using a two-sided two-sample stratified log-rank test. We will also describe the treatment effects in terms of hazard rates of HBsAg-loss and corresponding 95% confidence intervals. To take into account the stratification at randomization, we will use stratified Cox proportional hazard models. Comparison of hazard rates of HBsAg loss across two treatment groups adjusting for other baseline demographic, virological and clinical characteristics such as age, race, genotype, HBeAg status, initial HBV DNA level, and baseline histology will be performed using Cox proportional hazard regression. The results will be presented as incidence rate ratios of HBsAg loss and 95% confidence intervals.

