8.2. Missing data

Primary analyses will be performed using all enrolled participants (intention-to-treat analysis). For the primary analysis, the proportion of patients with HBsAg loss at the end of follow-up (week 240) will be estimated using the product limit (Kaplan-Meier) method which includes drop outs for as long as they are followed. Since our sample size estimation accounts for participants lost to follow up for various reasons, and due to randomization, the rate of missing is expected to be similar in the two treatment groups, we will also conduct the analysis of primary endpoint on the available cases. For this analysis, we will describe the treatment effects in terms of relative risks and 95% confidence intervals. In order to take into account the stratification at the randomization, we will use Mantel-Haenszel chi-square test. Comparison of rates of HBsAg loss across two treatment groups adjusting for other baseline demographic, virological and clinical characteristics such as age, race, genotype, HBeAg status, initial HBV DNA level, and baseline histology will be performed using multivariable log-linear (Poisson) regression, with HBsAg loss (Yes/No) as the outcome. The results will be presented as relative risks of HBsAg loss and their 95% confidence intervals.

In general, the procedure of missing outcome data will be handled as follows in statistical analyses. First, we will explore the pattern of missing data by comparing characteristics of participants with available data to those with missing data. For data missing completely at random (does not depend on observed outcome; MCAR) standard analytical techniques described earlier would produce unbiased results when the analysis is performed on the complete data. For the time-to-event data analyses, the analytical methods such as Kaplan-Meier method, log-rank test, and Cox proportional hazard model automatically accounts for MCAR drop-outs. However, in other cases, we will assume that the dropout depends on observed outcome and/or covariates (missing at random, MAR). For such scenarios, likelihood-based methods such as mixed models, generalized linear mixed models and logistic regression will provide unbiased inference. For GEE, we will draw inference using inverse-probability-weighting approach, with models fitted using the reciprocal of the estimated probability of missing as weights. The probability of missing will be estimated using logistic regression.

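### The primary test of week-240 HBsAg loss leaves out the randomisation strata: valid, but mildly conservative if the strata are prognostic

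*Combined protocol and SAP*

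**What the plan says.** Section 3 (Study design), like the Synopsis, sets the strata: "Enrolled participants will be stratified by HBeAg status (positive/negative), known genotype (A vs. all others) and cirrhosis (present vs. absent"). Three two-level factors give eight cells.

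Section 8.1 defines the primary population: "Primary analyses will be performed using all enrolled participants (intention-to-treat analysis"). Section 8.1.1 estimates loss at week 240 by Kaplan-Meier and gives the test: "HBsAg loss between two treatment groups will be compared using a Wald-type two-sided two-sample proportion test (chi-square test"). It names no strata.

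The strata enter elsewhere:

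- **Section 8.2 (Missing data).** For a supplementary analysis, "we will also conduct the analysis of primary endpoint on the available cases". Within it, "In order to take into account the stratification at the randomization, we will use Mantel-Haenszel chi-square test". A covariate-adjusted Poisson model belongs to the same analysis.
- **Section 8.1.2 (secondary endpoint 2.2.1a).** For cumulative loss over time, "HBsAg loss between two treatment groups will be compared using a two-sided two-sample stratified log-rank test", with stratified Cox models.
- **Section 8.1.2.1 (other binary secondary endpoints).** A Mantel-Haenszel test is planned. The event list omits HBsAg loss, although the sentence on adjusted regression names it as the outcome.

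The sample size in Section 8.3 (Sample size and power) was found "using a two-sided test of equality between two proportions (chi-square test"), also unstratified.

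**The concern.** Stratified allocation balances the arms within each stratum, so differences between strata no longer contribute to the random error of the treatment comparison. An unstratified standard error still counts them. If HBeAg status, genotype or cirrhosis predicts HBsAg loss, the planned standard error is larger than the true one. The test then rejects less often than 5% under the null, and the confidence interval is too wide.

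The plan recognises this in its supplementary and secondary analyses but not in the test that decides the trial, and it gives no reason. Someone wanting a stratified comparison of the week-240 proportion would have only the available-case one, although about 25% loss to follow-up is expected.

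The documents hardly say whether the strata are prognostic. The Background reports, for one tenofovir study, that HBsAg loss was 3% after one year and "this figure increased to 6% after 2 years of therapy (only in genotypes A and D"). Genotype D falls in the other stratum, which blurs the contrast.

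**Working it through.** **1. The plan's own figure.** Inputs from Section 8.3 (Sample size and power): 5% versus 15%, two-sided 5%, 80% power. With pooled variance under the null,

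n = [1.960·√(2·0.10·0.90) + 0.842·√(0.05·0.95 + 0.15·0.85)]² / 0.10² = 140.1, rounded up to 141 per arm.

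Then 282/0.75 = 376. Both figures reproduce, and power at 141 per arm is 80.3%.

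**2. The mechanism in one worked case.** Assume 20% genotype A, five times the loss rate in genotype A, and 10% loss overall in both arms.

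- Rate in others: 0.10/(0.2·5 + 0.8) = 0.0556. Rate in genotype A: 0.2778.
- Variance counted by the unstratified test: 0.10·0.90 = 0.0900.
- Variance left after balancing: 0.2·0.2778·0.7222 + 0.8·0.0556·0.9444 = 0.0821.
- Ratio of true to counted standard error: √(0.0821/0.0900) = 0.955.
- Actual type I error: 2·[1 − Φ(1.960/0.955)] = 4.0%, not 5%.

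Simulation of this case (282 evaluable, no censoring) gave 4.2% for the Wald form, 4.0% for the pooled chi-square and 5.0% for Mantel-Haenszel.

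**3. Simulation without censoring.** 282 evaluable, exact balance within strata, 100,000 trials per setting. Assumed genotype A 20%; where eight cells are used, HBeAg-positive 50% and cirrhosis 10%. Planned Wald test versus Mantel-Haenszel:

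| Assumed rate ratios | Type I error, 10% null | Power, 5% vs 15% |
|---|---|---|
| None (8 cells) | 5.2% vs 5.0% | 83.0% vs 82.3% |
| Genotype A ×3 | 4.7% vs 4.9% | 82.9% vs 83.3% |
| Genotype A ×3, HBeAg ×2 (8 cells) | 4.6% vs 5.0% | 83.3% vs 84.1% |
| Genotype A ×5 | 4.2% vs 5.0% | 83.7% vs 85.3% |
| Genotype A ×10 | 3.2% vs 4.9% | 85.2% vs 89.1% |

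**4. Simulation under the trial's conditions.** 188 per arm on average, exponential dropout to 25% at week 240, 12-week visits, 40,000 trials per setting. Assumed: genotype A 10, 20 or 30%; HBeAg-positive 50%; cirrhosis 10% and not prognostic; blocks of 4; a common treatment odds ratio (OR) across strata. The Monte Carlo standard error is 0.11 point for type I error and 0.17 for power. Planned Wald test with Greenwood variances versus the stratified Kaplan-Meier test described under the fix:

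| Strata | Type I error (5% and 10% nulls) | Power, 5% vs 15% | Change (points) |
|---|---|---|---|
| Not prognostic | 4.9–5.3% vs 4.9–5.2% | 87.1% vs 86.5–86.9% | −0.3 to −0.6 |
| Genotype A OR 2 | 4.9–5.1% vs 4.9–5.1% | 86.9–87.4% vs 86.7–87.1% | −0.2 to −0.3 |
| Genotype A OR 4, HBeAg OR 2 | 4.4–5.0% vs 4.9–5.2% | 87.3–87.5% vs 87.6–88.2% | +0.3 to +0.7 |
| Genotype A OR 10 | 3.9–4.5% vs 5.0–5.1% | 88.3–88.5% vs 89.9–90.4% | +1.6 to +2.0 |
| Genotype A OR 37 (extreme) | 2.3–4.2% vs 5.1–5.2% | 89.3–90.2% vs 92.7–95.1% | +3.4 to +4.9 |

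With blocks of 2 or 10% dropout (20,000 trials per setting) the change is −0.2 to −0.7 (not prognostic), +0.2 to +0.7 (OR 4 and 2) and +1.3 to +2.3 (OR 10). Reading the planned test as a pooled-variance chi-square lowers its power by 0.2 to 0.3 point and its type I error by about 0.1.

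**5. Source of the gain.** When the two tests are set to the same type I error, their power differs by only −0.5 to +0.4 point.

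**6. Interval coverage at 5% versus 15%.** Planned interval 94.6–97.2%; stratified with pooled-arm variance 94.9–95.4%; stratified with arm-specific Greenwood variances 92.5–94.3%. The last falls short because 95–98% of trials have a stratum with events in only one arm.

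**The case against.** No error is at stake. The planned test is valid, agrees with the sample-size method and exceeds its power target. The plan follows a recognisable pattern of a simple primary test with stratified analyses in support. The stratified log-rank and Cox analyses in Section 8.1.2 are not restricted to available cases and concern the same event, so the strata are not ignored throughout. The sign of the benefit is unknown, since the documents give no stratum shares or rates, and the strongest scenarios have no documentary basis. All of this stands, and it is why the point is optional.

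Two things remain. A log-rank or Cox comparison of time to loss does not test the week-240 proportion. And the stratified test of that proportion does leave out the dropouts.

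The remedy is also open to challenge. It is less familiar than a two-sample test, and some strata will be tiny: 376·0.5·0.1 times 10, 20 or 30% gives 1.9, 3.8 or 5.6 expected participants for genotype A with cirrhosis in each HBeAg group. In a 2,000-trial check at 10% genotype A, one-participant strata arose about 0.57 times per trial, where the variance term reads 0/0. In about 26% of trials follow-up in some stratum-arm ended before week 240. The first is settled by giving such strata zero weight and the second by a carry-forward rule. Type I error stayed near 5% in that check. The added complexity is real and is a fair reason to prefer the smaller change.

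**Conclusion.** The point holds, as a minor matter of efficiency. The deciding test leaves out the factors used to randomise, and the only stratified test of the same proportion is on available cases. The planned test remains valid. If the strata are prognostic it is conservative, at a cost of 0.3 to 0.7 point of power for moderate strata and 1.6 to 2.0 for strong ones. If they are weak or not prognostic, stratifying costs 0.2 to 0.6 point, or up to 0.7 with blocks of 2. With rate ratios and no censoring the gains are somewhat larger, for example 85.3 − 83.7 = 1.6 points at genotype A ×5.

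These sizes rest on assumed stratum shares, stratum effects and block size, none of which the documents give. The extreme row carries no weight in this conclusion. The sample size needs no change.

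**What to change.** In Section 8.1.1, make the primary test a stratified comparison of the week-240 Kaplan-Meier proportions in all randomised participants, over the eight strata as recorded at randomisation. In each stratum let n1 and n0 be the numbers randomised, n = n1 + n0, d the difference in Kaplan-Meier estimates, and V the Greenwood variance of the Kaplan-Meier estimate with both arms pooled. With w = n1·n0/n,

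Z = Σ(w·d) / √Σ[n1·n0·V·n/(n−1)].

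With no censoring, let m1 and m0 be the stratum's totals with and without loss. Then V = m1·m0/n³ and each variance term becomes n1·n0·m1·m0/[n²(n−1)]. This is exactly the Mantel-Haenszel test already planned in Section 8.2, so the change extends that test to all randomised participants. The n/(n−1) factor matters: without it type I error was 5.1–5.75%, with it 4.9–5.2%.

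Report Σ(w·d)/Σw with a 95% confidence interval from the same variance. State two rules:

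- A stratum filled in only one arm, including a stratum of one participant, contributes zero to both sums. Under the assumed shares this affects on average 0.1 to 0.9 of the 376 participants.
- If follow-up in a stratum-arm ends before week 240, its last Kaplan-Meier value is carried forward.

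Keep the unstratified Wald test as a sensitivity analysis. If the sponsor prefers not to alter the primary test, prespecifying this stratified version as a sensitivity analysis in all randomised participants would fill the gap left by Section 8.2.

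The cost is a paragraph of SAP wording, some programming and the justification of an amendment, which should be fixed without sight of outcomes by arm. No new data or participants are needed.
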